### Step-by-step process

1. Stop the interview/activity
2. Express concern for participant’s safety and well-being and the importance of getting participant the help they need to get through this difficult time (see script above)
3. Encourage the participant to call the hotline and/or offer to call together:
- Toll-free, 24-hour hotline of the **National Suicide Prevention Lifeline [name]**  
Your call will be connected to a trained counselor at a suicide crisis center nearest you.[https://suicidepreventionlifeline.org/?utm\\_source=google&utm\\_medium=web&utm\\_campaign=onebox](https://suicidepreventionlifeline.org/?utm_source=google&utm_medium=web&utm_campaign=onebox)
4. If the participant won’t call and/or disconnects the call and won’t reconnect, and you are concerned they are in imminent danger of hurting themselves or others, stay on the phone with them and ask them to “hold while you make a call to get some help to them.”
5. Call 9-1-1 and request a CIT officer make a welfare check on an individual expressing an imminent desire to kill themselves. Cooperate with the 91-1 operator to provide details about participant’s location and specific

statements that caused you to believe the individual was at imminent risk of suicide.

6. If the participant is still on the phone, reassure them that you will stay on the phone until the help arrives. Wait with the participant on the line until they confirm the CIT officer has arrived at their location.

7. Immediately following a referral to the suicide prevention lifeline or a 9-11 welfare check call:

- If in TTRP, inform TTRP supervisor on-call and inform them of the situation
- If not in TTRP, call [name] at [contact] (cell) and inform her of the situation

8. After you provide participant support and have informed either the TTRP supervisor or [name], document the incident in RedCap in the participant's file.

9. The day following the incident, attempt to call the participant to follow up and schedule next study visit and/or leave a message requesting participant reach out when able.

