## PROTOCOLS FOR SUICIDAL PARTICIPANTS:

### Acute Suicidal Warning Signs

- The participant expresses hopelessness (e.g., “I’ll never get better”).
- The participant makes direct or indirect statements about killing themselves, being better off dead, or things being better for others if participant wasn’t alive

If any participant makes a direct or indirect statement about suicide, hopelessness or death, even when said in a joking or off hand manner, this is a cause for concern. Sometimes suicidal people leave hints. It is not true that a person who talks frequently about committing suicide will not do it. Some keep their suicidal thoughts to themselves, while others do not. If a participant shows a desire or intent to kill her/him/their self, s/he/they should be evaluated by a qualified clinician to determine her/his/their level of risk and be connected to treatment setting that can ensure their safety. If you suspect that a person is in danger of killing her/him/their self, the interview should be stopped and specific focus should be made on the participant’s safety, and the protocol below should be followed:

To start, you should say:

*“I am concerned about what you just said to me about your feelings/thoughts right now (e.g., “feeling so bad that you wish you were dead” or “thinking things are hopeless or would be better if you weren’t around”). I think this is really important. I need to connect you with someone to talk to who can help. I can give you the National Suicide Prevention Lifeline number for you to call privately, or we can do it together if that would be helpful.”*

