**The following statement has been included in the Informed Consent form so that participants are aware of this protocol:**

*What will happen if the research team thinks I am suicidal?*

*If, while we are interacting with you, any member of our research team or smoking cessation staff is concerned that you are in danger of killing yourself, you will be encouraged to call the National Suicide Prevention Lifeline or 9-1-1. If you do not agree to voluntarily call the Suicide Prevention Lifeline or 9-1-1, the study protocol requires the research team and/or staff member to call 9-1-1 and request a CIT officer provide a welfare check to ensure your safety.*

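### The consent statement says a 9-1-1 call is required whenever a participant in suicidal danger declines to call; the protocol's steps direct it only if danger is imminent, and otherwise arrange no clinician evaluation

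*Protocol*

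**What the plan says.** All of this is current text in Protocol Section N, under the protocols for suicidal participants.

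- **Entry and evaluation (Acute Suicidal Warning Signs).** Staff stop the interview and follow the steps once they suspect danger of suicide; imminence is not needed. A participant who shows desire or intent "should be evaluated by a qualified clinician to determine her/his/their level of risk" and be linked to a treatment setting.
- **Step 4 (Step-by-step process).** This has two conditions joined by *and*. The participant will not "call and/or disconnects the call" and does not reconnect; "and you are concerned they are in imminent danger of hurting themselves or others".
- **Step 5.** Staff call 9-1-1 and "request a CIT officer make a welfare check on an individual expressing an imminent desire to kill themselves". They give the operator the "statements that caused you to believe the individual was at imminent risk of suicide".
- **Consent statement.** This is included to make participants aware of the protocol. It applies when any team member "is concerned that you are in danger of killing yourself". It continues: "If you do not agree to voluntarily call the Suicide Prevention Lifeline or 9-1-1", then "the study protocol requires the research team and/or staff member to call 9-1-1" and ask for a welfare check.

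**The concern.** The consent statement presents itself as a description of the protocol and uses the word *requires*, but the rule it gives is not the rule in the steps. Two things are at stake.

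The first is the accuracy of consent. Participants should be told correctly when staff must send police to them.

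The second is safety. If a participant declines to call and staff do not judge the danger imminent, the consent statement points to one response and the steps to another. The response that the warning-signs text does call for, evaluation by a qualified clinician, is not assigned to anyone in the numbered steps. Staff working from the steps alone have no instruction to obtain it.

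**Working it through.** No arithmetic applies beyond counting. The check sets the two triggers side by side and then follows each kind of participant through both.

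**Conditions for the 9-1-1 call**

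| Condition | Steps 4–5 | Consent statement |
|---|---|---|
| Danger of suicide suspected | Needed (entry to the steps) | Needed |
| Imminence | Needed; 3 mentions (danger, desire, risk) | Not needed; 0 mentions |
| What the participant does | Will not call, or disconnects and will not reconnect | Does not agree to call |
| Danger to others | In step 4, not in step 5 | Not mentioned |

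**Outcome by case** (in every case staff already suspect danger of suicide, since otherwise the steps do not start)

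| Case | Steps | Consent statement | Result |
|---|---|---|---|
| 1. Declines; danger imminent | Call | Call required | Agree |
| 2. Declines; danger not imminent | No call directed | Call required | **Conflict** |
| 3. Agrees, hangs up, will not reconnect; danger imminent | Call | Depends on whether refusing to reconnect counts as not agreeing to call | Unclear |
| 4. Declines; others also in imminent danger | Call under step 4; step 5 describes suicide only | Call required | No undisclosed call; steps 4 and 5 differ from each other |

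Case 2 is a contradiction on any reading. Case 3 is a gap in clarity. Case 4 is an inconsistency inside the steps.

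**The case 2 participant, step by step**

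- Steps 1 to 3: the activity stops, concern is expressed, and the hotline is offered. The participant declines.
- Steps 4 to 6: not triggered, because imminence is absent.
- Step 7: notification of the TTRP on-call supervisor or the study contact follows a Lifeline referral or a welfare-check call. It applies if offering the number counts as a referral.
- Steps 8 and 9: the incident is documented after that notification, and the participant is telephoned the next day.

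None of the nine steps is an evaluation by a clinician or an instruction to arrange one. The Participant Safety Monitoring Plan names a licensed psychologist who trains the team and can be consulted about the protocols, but no step tells staff to contact that person about a case.

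**The case against.** Five points can be made on the other side.

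1. *The mismatch over-warns.* On imminence the consent statement announces more police calls than the steps direct, so this difference alone cannot produce a call that a participant was not told about. The steps also do not forbid a call at a lower level of concern. Both points are right, and they limit the harm. They do not make the statement accurate, because it says the protocol requires something that the protocol leaves undirected.

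2. *It is a plain-language summary.* Section J sets a 4th-grade reading level. Even so, *immediate danger* is plain language, and a definite *requires* goes beyond loose paraphrase.

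3. *The steps reach further than consent on disconnection and danger to others.* A reader might infer that staff can send police on grounds never disclosed. The documents do not support that. Anyone at step 4 is already suspected to be in danger of suicide, which is the consent statement's own danger condition, and step 5 words the call for suicide only. Danger to others is therefore not shown to be a separate, undisclosed trigger. Refusing to reconnect can fairly be read as not agreeing to call. Both remain minor wording points.

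4. *Follow-up exists.* Step 3 offers a crisis-line counselor with staff on the call, step 7 may bring in a supervisor, and step 9 is a next-day call. This is real support, but it is not the evaluation that the warning-signs text asks for. The TTRP works under its own IRB-approved protocol, which is not among the documents and might arrange an evaluation for contacts made there.

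5. *The full form is not visible.* Only the one reproduced statement can be read; the rest of the consent form was removed before review. This limits what can be said about omissions. It does not affect the contradiction on imminence, which lies within the reproduced statement.

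**Conclusion.** The concern holds for imminence. For a participant who declines to call and is in danger that is not imminent, the consent statement says a 9-1-1 call is required and the steps direct none. For the same participant, no numbered step arranges the clinician evaluation that the protocol says should take place. Disconnection and danger to others are lesser points: the first is unclear wording in the consent statement, the second a disagreement between steps 4 and 5.

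The size is one clear conflict, one unclear case and one internal inconsistency. The statement is meant for all 20 planned participants (25 budgeted). The documents give no basis for estimating how many would meet either trigger. Endpoints, sample size and analysis are unaffected, so this is a matter of consent accuracy and participant safety that should be corrected, not a threat to the study's results.

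The conclusion assumes that the reproduced statement is the form's operative text on this point and that step 4's *and* means what it says. The finding on evaluation covers only the steps printed in this protocol.

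**What to change.** Use one trigger in both places.

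- **Default: reword the consent statement.** For example: *If you do not agree to call, or you end the call and do not reconnect, and we are concerned you are in immediate danger of hurting yourself, the study protocol requires us to call 9-1-1 and request a welfare check.*
- **Alternative.** If the study's clinical resource prefers the broader rule, remove the imminence condition from steps 4 and 5 (all three mentions), and still add disconnection to the consent statement.
- **Danger to others.** Either drop it from step 4, or add it to step 5 and to the consent statement.
- **One new numbered step.** If the participant declines to call and danger is not judged imminent, staff notify the TTRP on-call supervisor or the study contact already named in step 7. That person arranges the clinician evaluation, consulting the clinical resource as needed.

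The cost is an IRB-approved wording amendment to the protocol and consent statement and a short update to staff training. The contacts are already named, though arranging an evaluation adds a task to their role. Data collection, endpoints, sample size and analysis do not change.

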**The following statement has been included in the Informed Consent form so that participants are aware of this protocol:**

*What will happen if the research team thinks I am suicidal?*

*If, while we are interacting with you, any member of our research team or smoking cessation staff is concerned that you are in danger of killing yourself, you will be encouraged to call the National Suicide Prevention Lifeline or 9-1-1. If you do not agree to voluntarily call the Suicide Prevention Lifeline or 9-1-1, the study protocol requires the research team and/or staff member to call 9-1-1 and request a CIT officer provide a welfare check to ensure your safety.*

**O. Data Sharing**

De-identified data will be made available to outside investigators upon request. However, it is noteworthy that data collected as part of the current proposal will be from a small sample, and will not provide sufficient information from which to draw conclusions. Rather these data will support a larger, adequately powered trial, from which data may be more complete and useful to other investigators.

**P. Confidentiality**

**General Procedures:** Each participant will be assigned an identification number that will be utilized in place of names in all electronic and print data files. The file containing the links between participant names and identifiers will be kept in a separate password-protected file, which will be destroyed 12 months after the completion of the study. Any print information will be stored in a locked filing cabinet in the Principal Investigator's locked office. Electronic data (with names omitted) will be maintained on the investigator's computers, and all computers and electronic files will be password protected. Biochemical verification of smoking

status will be collected in a private room in the TTRP. All project staff will complete extensive training focused on each of the following topics: 1) project rationale and objectives, 2) the informed consent process, 3) general data collection procedures (e.g., computer data collection, privacy), and 4) use of the carbon monoxide monitor.

Minimizing risk of loss of participant confidentiality and data storage procedures:

All information obtained from participants will be kept completely confidential. Data will be stored as follows:

- All data will be stored in secure locations to minimize the risk of breach of confidentiality, including locked file cabinets and password-protected computers and databases. Adverse events will be reported to the University of Oklahoma Health Sciences Center IRB, as appropriate, to ensure the safety of subjects' information.
- All study questionnaires will be administered online with participants' own devices or a study device using an electronic data capture system (REDCap) to maintain 21 CFR Part 11 compliance and Good Clinical Practice (GCP) standards.
- All transcripts from interviews will be stored on encrypted hard drives disconnected from the Internet and kept in locked file cabinets.
- Human subjects will be assigned coded participant ID numbers.
- Files with identifying information will be stored separately from files with other forms of data (e.g., substance use status, mobility data, transcripts).
- Access to individually identifiable private information about human subjects will be had only by the individuals listed in this proposal.
- Study investigators have completed required University of Oklahoma Health Science Center training and certification in the conduct of research with human subjects.

## **Single-arm pilot trial analytic plan**

**NCT05365633**

### **“Empowering sexual and/or gender minority tobacco cessation: A pilot study”**

**Document date: January 1, 2021**

**Sample Size/Analysis Plan.** Primary outcome variables will be: retention, perceptions of the intervention, adaptive coping strategies, biochemical verification of tobacco abstinence at 12 weeks post-quit-date, and treatment adherence. We will evaluate retention by calculating the proportion of participants who complete the final study visit at 12-weeks post-quit, with the goal of retaining >80% of participants. We will qualitatively evaluate perceptions of the intervention (as described above). We will use a two-sided paired samples t-test to examine the mean differences in adaptive coping strategies pre- and post-intervention ( $\alpha=0.05$ ). Assuming a standard deviation of differences of 4.0^80 we will have 80% power to detect a mean difference of 2.6 in adaptive coping strategies. Tobacco cessation outcomes will be considered successful if the proportion of participants with biochemically-verified smoking abstinence (expired carbon monoxide) at 12 weeks post-quite-date is equal to or greater than the general TTRP intervention (i.e., 18% at 12 weeks). Treatment adherence will be considered successful with moderate/optimal medication and counseling adherence >50% of treatment weeks.

**Expected outcomes.** Empowerment-enhanced tobacco cessation assistance will be acceptable and feasible (Aim 1), will increase within-subject empowerment outcomes (Aim 2), and will meet benchmarks for tobacco cessation outcomes (Aim 3).
